## 8 Safety and Adverse Events

## 8.1 Definitions

## **Unanticipated Problems Involving Risk to Subjects or Others**

Any incident, experience, or outcome that meets all of the following criteria:

• Unexpected in nature, severity, or frequency (i.e. not described in study-related documents such as the IRB-approved protocol or consent form, the investigators brochure, etc)

- Related or possibly related to participation in the research (i.e. possibly related means there is a reasonable possibility that the incident experience, or outcome may have been caused by the procedures involved in the research)
- Suggests that the research places subjects or others at greater risk of harm (including physical, psychological, economic, or social harm).

## **Unanticipated Adverse Surgical procedure Effect**

An Unanticipated Surgical procedure Effect is any serious adverse effect on health or safety, or any lifethreatening problem or death caused by, or associated with a surgical procedure, if that effect, problem, or death was not previously identified in nature, severity, or degree of incidence in the investigational plan or application (including a supplementary plan or application), or any other unanticipated serious problem associated with a that relates to the rights, safety, or welfare of subjects.

## Serious injury

Any injury or illness that is any one of the following:

- Life-threatening
- Results in permanent impairment of a body function or permanent damage to body structure
- Necessitates medical or surgical intervention to preclude permanent impairment of a body function or permanent damage to a body structure

## **Adverse Event**

An adverse event (AE) is any symptom, sign, illness or experience that develops or worsens in severity during the course of the study. Intercurrent illnesses or injuries should be regarded as adverse events. Abnormal results of diagnostic procedures are considered to be adverse events if the abnormality:

- Results in study withdrawal
- Is associated with a serious adverse effect related to the surgical procedure
- Is associated with clinical signs or symptoms
- Leads to additional treatment or to further diagnostic tests
- Is considered by the investigator to be of clinical significance

#### What will be monitored:

**Stopping rules**: Any unanticipated effects and all adverse effects resulting in research subject death or injury will be reported to the PI immediately, no later than 10 days after the event and will include:

- 1. Maternal sepsis with admission to ICU attributable to the cerclage placement
- 2. Maternal death attributable to the cerclage placement
- 3. Maternal bleeding requiring blood transfusion attributable to cerclage placement

4. Fetal and/or neonatal death or injury attributable to the cerclage placement

Frequency of monitoring reports: after approximately 50% of the subjects have delivered

# 8.2 Recording of Adverse Effects

At each contact with the subject, the investigator must seek information on adverse effects by specific questioning and, as appropriate, by examination. Information on all adverse surgical procedure effects should be recorded immediately in the source document, and also in the appropriate adverse effect module of the case report form (CRF). All clearly related signs, symptoms, and abnormal diagnostic procedures results should recorded in the source document, though should be grouped under one diagnosis.

All adverse effects occurring during the study period must be recorded. The clinical course of each event should be followed until resolution, stabilization, or until it has been determined that the study treatment or participation is not the cause. Serious adverse effects that are still ongoing at the end of the study period must be followed up to determine the final outcome. Any serious adverse effects that occur after the study period should be recorded and reported promptly (see section 8.3 below).

The minimum initial information to be captured in the subject's source document concerning the adverse effect includes:

- Study identifier
- Subject number
- A description of the event
- Date of onset
- Investigator assessment of the association between the event and study treatment
- Current status
- Whether study treatment was discontinued
- Whether the event is serious and reason for classification as serious

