# 5.2.2 Expectant management

For those randomized to expectant management, they will continue routine pregnancy care: daily vaginal progesterone and surveillance for signs of preterm labor.

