## 7.2 Statistical Methods

The primary outcome is spontaneous preterm birth before 34 weeks of gestation. Secondary outcomes include gestational age at delivery, interval between diagnosis and delivery, birth weight, spontaneous preterm birth rates at less than 24, 28, 32 and 37 weeks gestation and spontaneous rupture of membranes at less than 34 weeks gestation. Secondary safety outcomes include admission to NICU, neonatal death, length of stay in the NICU until discharge home, composite adverse neonatal outcome that includes necrotizing enterocolitis (stage 3 or 4), intraventricular hemorrhage (grade 3 or 4), respiratory distress syndrome (grade 3 or 4), need of intubation and mechanical ventilation, retinopathy of prematurity requiring laser treatment (stage 3 or 4) and proven sepsis requiring treatment), and significant adverse maternal effects will include: intraoperative rupture of membranes, clinical or histological chorioamnionitis, postpartum hemorrhage, cervical tear and uterine rupture). Neonatal mortality prior to discharge home form the hospital.

Statistical analysis will be based on the intention-to-treat principle. Comparisons between the two groups will be made with the Mann-Whitney U test. Univariate comparisons of dichotomous data will be performed with Fishers exact test. The p values for all hypotheses will be two sided, and p values of less than 0.05 will be considered to be significant. The risk of spontaneous preterm birth before 34 weeks will be quantified by use of the relative ratio and 95% confidence interval. Multivariate analysis will be performed using logistic regression. The risk of spontaneous preterm birth from randomization until delivery will be assessed with Kaplan-Meier analysis, in which gestational age is the timescale, spontaneous delivery is the event, and elective deliveries are censored. SPPS software package (version 16.0) will be used for all statistical analyses.

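### Adverse event follow-up may end on an unblinded judgement that study treatment is not the cause, so the course and outcome of events may be traced unequally between arms

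*Combined protocol and SAP*

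**What the plan says.** Section 8.2 sets the follow-up rule. Each event is followed "until resolution, stabilization, or until it has been determined that the study treatment or participation is not the cause". The three ends are alternatives, so any one of them closes the event.

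The same section sets a wide duty to record: "All adverse effects occurring during the study period must be recorded". It requires active enquiry: "At each contact with the subject, the investigator must seek information on adverse effects by specific questioning". For serious events it adds: "Serious adverse effects that are still ongoing at the end of the study period must be followed up to determine the final outcome". None of these three sentences depends on arm or cause.

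The judgement that can close an event belongs to the investigator. The minimum initial information listed in 8.2 includes "Investigator assessment of the association between the event and study treatment". No blinded assessor is described, and section 3.1 makes the trial open-label.

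The Study Summary names cervical cerclage as the study product and standard care with vaginal progesterone as the reference therapy. Of women allocated to expectant management, section 5.2.2 says "they will continue routine pregnancy care: daily vaginal progesterone and surveillance for signs of preterm labor".

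**The concern.** A rule that ends follow-up on attribution works differently in two arms when only one arm has a study procedure. Section 1.3 names bleeding, chorioamnionitis and cervical laceration as risks of cerclage. If a woman with a suture bleeds, the investigator will find it hard to rule the cerclage out, so the event stays open until it resolves or stabilises. If a control woman bleeds, there is no suture to blame. The attribution is requested with the first record of the event, so follow-up could end early.

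At stake is the comparability of what is known about an event after its onset: how long it lasted, how severe it became and how it ended. Under 8.4 the principal investigator oversees safety, and under 8.4.1 the DSMB reviews safety data once about half the subjects have delivered. Unequal tracing could make cerclage look worse on severity and outcome when true risks are equal. It would also let a real excess with cerclage be dismissed as an artefact of closer follow-up.

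**Working it through.** **Figures in the plan.** There are none on this point: no adverse event rate, and no share of events expected to be closed on attribution. The sample size in 7.1 (93 per arm for 70% versus 50%, two-sided 5%, 80% power) reproduces with the usual two-proportion formula without continuity correction. It concerns the primary endpoint only and does not enter here.

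**Step 1: is the third end easier to reach in controls?** The Study Summary defines the study product as cerclage. Sections 3.1 and 4.3 offer progesterone as standard care at a cervical length of 25 mm or less, outside randomisation. On that reading, an event in a control woman without a cerclage cannot be caused by study treatment. Participation must also be ruled out. For controls this consists of consent, monthly contacts (6.3), record abstraction (6.5) and the allocation itself. The end is therefore easier to reach in controls, though not automatic.

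**Step 2: what else would catch later worsening of a closed event?**

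- Section 8.1 counts worsening in severity as an adverse event, and 8.2 requires all to be recorded.
- Section 6.3 gives both arms the same monthly contact. Appendix #2 asks every woman again about complications, bleeding, discharge, contractions, leaking fluid and admissions. It has no item on the severity or outcome of an event already reported, and none on fever.
- The adverse effects paragraph preceding 8.3.2 requires any effect resulting in serious injury or death to be reported within 24 hours, without a causality condition.
- The 8.2 sentence on serious effects covers those still ongoing at study end. It does not reopen a non-serious event closed earlier.
- Section 6.5 abstracts pregnancy outcome, and neonatal outcome to discharge, from records for all subjects.

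**Step 3: which results depend on length of follow-up?** The neonatal safety endpoints in 3.3 and 7.2 come from records. The maternal list in 7.2 ("significant adverse maternal effects will include: intraoperative rupture of membranes, clinical or histological chorioamnionitis, postpartum hemorrhage, cervical tear and uterine rupture") counts whether named events occur. What is exposed is the course, peak severity and final outcome of events closed before study end.

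**Step 4: illustration, on assumptions only.** Let the true risk of an event that later worsens be equal in the two arms. Let s be the share of control events closed at onset, and r the share of later worsening in closed events that another route catches. Assume no cerclage-arm event is closed early. The recorded control risk is the true risk × [1 − s(1 − r)], so the recorded ratio, cerclage to control, is

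RR = 1 / [1 − s(1 − r)].

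| s | r = 0 | r = 50% | r = 90% |
|---|---|---|---|
| 25% | 1/0.75 = 1.33 | 1/0.875 = 1.14 | 1/0.975 = 1.03 |
| 50% | 1/0.50 = 2.0 | 1/0.75 = 1.33 | 1/0.95 = 1.05 |
| 90% | 1/0.10 = 10.0 | 1/0.55 = 1.82 | 1/0.91 = 1.10 |

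Closing some cerclage-arm events early as well shrinks the ratio. With half of them closed, s = 90% in controls and r = 50% in both arms, it is (1 − 0.5 × 0.5)/(1 − 0.9 × 0.5) = 0.75/0.55 = 1.36 rather than 1.82.

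The column r = 0 supposes that every route in Step 2 fails. The documents fix neither s nor r, so the table shows only how strongly the answer depends on the other routes.

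**The case against.** The strongest reply is that closing an event does not end the duty to notice it getting worse. Worsening is a new adverse event, every adverse effect must be recorded, both arms are questioned monthly on the same form, and serious injury or death is reported regardless of cause. The number and type of events, which 8.4 monitors, are largely set at recording. No planned endpoint is defined by the course of an adverse event. Ruling out participation as a cause is also a real condition: section 5.2 itself recognises that women may see either allocation as carrying unacceptable risk.

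Most of this stands, and it defeats three inferences a reader might draw. One is that nearly every control event would be closed on the first day; the text permits early closure but does not make it automatic. The second is that worsening harms would be seen mainly in the cerclage arm; that needs a high share of early closures and near failure of every other route. The third is that the safety comparison as a whole is biased; the neonatal endpoints do not pass through this rule, and the maternal endpoints count occurrences.

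The reply does not remove the asymmetry. The recording duty secures that an event is known, while the disputed clause governs how long it is traced. A new worsening still has to be detected, and the monthly form does not return to earlier events. Nearby wording leans the same way: the instruction on immediate entry reads "Information on all adverse surgical procedure effects should be recorded immediately in the source document", and all four events listed under the stopping rules in 8.1 are limited to those attributable to the cerclage.

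**Conclusion.** The concern holds in a limited form. Section 8.2 makes the length of adverse event follow-up depend on an unblinded causal judgement that is easier to make in the control arm. The course, peak severity and final outcome of events closed before study end may therefore be traced less completely in controls. This affects the adverse event data used for medical monitoring (8.4) and the DSMB review (8.4.1).

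The conclusion assumes that study treatment means cerclage, as the Study Summary indicates, and that investigators use the third alternative when it is available. The imbalance cannot be sized from the documents. In the illustration it runs from negligible to large, and the routes that remain open in both arms argue against the large end. The primary endpoint, the sample size and the record-abstracted neonatal endpoints are not affected. The weight is modest, but the defect is easily removed.

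**What to change.** In 8.2, delete the third alternative, so that causality no longer ends follow-up. State that every recorded event in either arm is followed to resolution, stabilisation or discharge after delivery, whatever its attribution. Leave the sentence on serious effects ongoing at study end as it is. Keep the investigator's causal assessment as a separate descriptive field that does not decide how long an event is followed.

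The cost is one deleted clause and some added chart follow-up of events that would now be closed early. Under 6.3 and 6.5, releases of medical information are signed at randomisation in both arms, so no new permission appears to be needed. The change concerns data collection only.

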#### **Adverse Effects**

Any adverse effect that results in serious injury or death, and any type of unanticipated adverse effect, regardless of seriousness or severity, must be reported to the principal investigator by telephone within 24 hours of the event.

Within the following 48 hours, the principal investigator shall provide further information, as applicable, on the unanticipated adverse event or the unanticipated problem in the form of a written narrative. This should include a copy of the completed Unanticipated Problem form, and any other diagnostic information that will assist the understanding of the event. Significant new information on ongoing unanticipated adverse effects shall be provided promptly to the principal investigator.

#### Deviations from the study protocol

Deviations from the protocol must receive both principal investigator and the investigator's IRB approval before they are initiated. Any protocol deviations initiated without principal investigator and the investigator's IRB approval that may affect the scientific soundness of the study, or affect the rights, safety, or welfare of study subjects, must be reported to the Principal investigator and to the investigator's IRB as soon as a possible, but no later than 5 working days of the protocol deviation.

#### Withdrawal of IRB approval

An investigator shall report to the principal investigator a withdrawal of approval by the investigator's reviewing IRB as soon as a possible, but no later than 5 working days of the IRB notification of withdrawal of approval.

#### 8.3.2 Investigator reporting: Notifying the IRB

#### **Adverse Effects**

All unanticipated effects and all adverse effects resulting in research subject death or injury reported by the investigator to the study Principal investigator must also be reported to the investigator's local IRB in accordance with their reporting requirements, though no later than 10 working days.

#### **Protocol Deviations**

Any protocol deviations initiated without principal investigator and/or the investigator's IRB approval that may affect the scientific soundness of the study, or affect the rights, safety, or welfare of study subjects, must be reported to the Principal investigator and to the investigator's IRB as soon as a possible, but no later than 5 working days of the protocol deviation.

Any adverse event that occurs any time during or after the research study, which in the opinion of the principal investigator is:

• Unexpected (An event is "unexpected" when its specificity and severity are not accurately reflected in the protocol-related documents, such as the IRB-approved research protocol, any applicable investigator brochure, and the current IRB-approved informed consent document

# AND

• Related to the research procedures (An event is "related to the research procedures" if in the opinion of the principal investigator, the event was more likely than not to be caused by the research procedures.)

The above is required regardless of whether the event is serious or non-serious, on-site or off-site

# **Adverse Effects**

All unanticipated effects and all adverse effects resulting in research subject death or injury must be reported to the investigator's local IRB in accordance with their reporting requirements, though no later than 10 working days.

## **Protocol Deviations**

Any protocol deviations initiated without principal investigator and/or IRB approval that may affect the scientific soundness of the study, or affect the rights, safety, or welfare of study subjects, must be reported to the investigator's IRB as soon as a possible, but no later than 5 working days of the protocol deviation.

## **Reporting Process**

Report unanticipated problems as defined above to the IRB office as a written report of the event (including a description of the event with information regarding its fulfillment of the above criteria, follow-up/resolution and need for revision to consent form and/or other study documentation).

Copies of each report and documentation of IRB notification and receipt will be kept in the Clinical Investigator's study file.

# **Other Reportable events:**

For clinical trials, the following events are also reportable to the IRB:

- Any adverse event that would cause the principal investigator to modify the protocol or informed consent form, or would prompt other action by the IRB to assure protection of human subjects.
- Information that indicates a change to the risks or potential benefits of the research, in terms of severity or frequency. For example:
  - An interim analysis indicates that participants have a lower rate of response to treatment than initially expected.
  - Safety monitoring indicates that a particular side effect is more severe, or more frequent than initially expected.
  - A paper is published from another study that shows that an arm of your research study is of no therapeutic value.
- Breach of confidentiality
- Change to the protocol taken without prior IRB review to eliminate apparent immediate hazard to a research participant.
- Incarceration of a participant when the research was not previously approved under Subpart C and the investigator believes it is in the best interest of the subject to remain on the study.
- Complaint of a participant when the complaint indicates unexpected risks or the complaint cannot be resolved by the research team.
- Protocol violation (meaning an accidental or unintentional deviation from the IRB approved protocol) that in the opinion of the investigator placed one or more participants at increased risk, or affects the rights or welfare of subjects.

# **Unanticipated Adverse Effects**

# Evaluation

The principal investigator shall immediately evaluate each Unanticipated Adverse Effect. Such evaluations shall be reported to the IRB office, and participating investigators, within 10 working days after the principal investigator first receives notice of the effect.

## Unreasonable risk to subjects

After evaluating an Unanticipated Adverse Effect, if the principal investigator determines the effect presents an unreasonable risk to subjects, the principal investigator shall terminate the study or parts of the study presenting that risk as soon as possible. Study termination shall occur no later than 5 working days after the principal investigator makes this determination and not later than 15 working days after the principal investigator first received notice of the effect.

## Withdrawal of IRB approval

The Principal investigator shall notify the IRB office and participating investigators of any withdrawal of approval of the study by a reviewing IRB within 5 working days after receipt of the withdrawal of approval.

# 8.4 Medical Monitoring

It is the responsibility of the principal Investigator to oversee the safety of the study. This safety monitoring will include careful assessment and appropriate reporting of adverse events as noted above, as well as the construction and implementation of a site data and safety-monitoring plan (see section 9 Auditing, Monitoring and Inspecting). Medical monitoring will include a regular assessment of the number and type of adverse events.

# 8.4.1 Data and Safety Monitoring Board

An independent Data and Safety Monitoring Board (DSMB) will review data relevant to safety (not efficacy) after approximately 50% of the subjects have delivered. The DSMB will provide a recommendation as to whether the study should continue without modification of the protocol or informed consent. All unanticipated problems involving risks to participants or others will be reported by [name] to the head of the DSMB for this study

# 9 Data Handling and Record Keeping

# 9.1 Confidentiality

Information about study subjects will be kept confidential and managed according to the requirements of the Health Insurance Portability and Accountability Act of 1996 (HIPAA). Those regulations require a signed subject authorization informing the subject of the following:

- What protected health information (PHI) will be collected from subjects in this study
- Who will have access to that information and why
- Who will use or disclose that information
- The rights of a research subject to revoke their authorization for use of their PHI.

In the event that a subject revokes authorization to collect or use PHI, the investigator, by regulation, retains the ability to use all information collected prior to the revocation of subject authorization. For subjects that have revoked authorization to collect or use PHI, attempts should be made to obtain permission to collect at least vital status (i.e. that the subject is alive) at the end of their scheduled study period.

